7.6.2. Action to be Taken if Pregnancy Occurs

Action to be Taken:

- The investigator will collect pregnancy information on any subject who becomes pregnant while participating in the study after administration of the *washout product*. The investigator will record pregnancy information on the appropriate form and submit it to GSKCH within 2 weeks of learning of the subject becoming pregnant. The subject will be followed to determine the outcome of the pregnancy. Information on the status of the mother and infant / neonate (including concomitant medications taken by the mother during the pregnancy) will be forwarded to GSKCH. Generally, follow-up will be no longer than 6 to 8 weeks following the estimated delivery date. Any termination of the pregnancy will be reported.
- While pregnancy itself is not considered to be an AE, any pregnancy complication or elective termination for medical reasons will be recorded as an AE or SAE.
- A spontaneous abortion is always considered to be an SAE and will be reported as such. An SAE occurring in association with a pregnancy, brought to the investigator's attention after the subject completed the study and considered by the investigator as possibly related to the investigational product, must be promptly forwarded to GSK.
- While the investigator is not obliged to actively seek this information in former study participants, he or she may learn of an SAE through spontaneous reporting.
- If the subject becomes pregnant during the study they should be withdrawn from the study and this should be recorded in the appropriate section of the CRF.

8. DATA MANAGEMENT

Data Management will be performed by GSKCH. For this study subject data will be entered into an electronic case report form, using a GSKCH validated data system.

Document Name	Clinical Protocol 207468.doc		
Type	Version	Document Identifier	Effective Date
eldo_controlled	3.0; Most-Recent; Effective; CURRENT	090032d580d15804	24-Mar-2017 07:31:33
Reason For Issue	Auto Issue		

8.1. Source Documents/ Data

The source documents (e.g. hospital records, clinical and office charts, laboratory notes, memoranda, subjects' diaries or evaluation checklists, pharmacy dispensing records, recorded data from automated instruments, microfiches, photographic negatives, microfilm or magnetic media, x-rays, subject files and records kept at the pharmacy, at the laboratory and at the medico-technical departments involved in the clinical study) which contain the source of data recorded in the CRF should be specified in the Source Document Designation Form. In some cases the CRF can be used as a source document.

Each subject will be assigned and identified by a unique Screening Number. Any reference made to an individual subject within the study must be done using the unique Screening Number.

8.2. Electronic Case Report Form

A CRF is a printed, optical, or electronic document designed to record all of the protocol required information to be reported to the sponsor on each trial subject.

For each subject who has given informed consent/assent and has been screened, CRF must be completed and signed by the Principal Investigator (or authorized designee) to certify that the data are complete and correct.

Management of clinical data will be performed in accordance with applicable GSKCH standards and data cleaning procedures to ensure the integrity of the data e.g. removing errors and inconsistencies in the data.

In order to protect the privacy of subjects, no Personally Identifiable Information (PII) (including the subject's name or initials or birth date) is to be recorded in the CRF or as part of the query text.

Adverse events and concomitant medications terms (if applicable) will be coded using MedDRA (Medical Dictionary for Regulatory Activities) and an internal validated medication dictionary, GSKDrug.

Subject data will be entered into GSKCH defined CRFs and transmitted electronically to GSKCH in a validated (21 CFR Part 11 compliant) web-based electronic data capture system (InFormTM).

Document Name	Clinical Protocol 207468.doc		
Type	Version	Document Identifier	Effective Date
elido_controlled	3.0; Most-Recent; Effective; CURRENT	090032d580d15804	24-Mar-2017 07:31:33
Reason For Issue	Auto Issue		

All CRF pages should be completed during a subject assessment when the CRF has been designated as the source. Data that is sourced elsewhere should be entered into the CRF in an agreed upon timeframe between the Investigator and Sponsor.

The CRFs (including queries, query responses and audit trails) will be retained by GSKCH. Site data archived compact discs (CD(s)) prepared by a third party will be sent to the investigator to maintain as the investigator copy following the decommissioning of the study.

8.3. Data Handling

Documentation of all data management activities should allow step-by-step retrospective assessment of data quality and study performance. Any changes or corrections to data will be performed in the Electronic Data Capture (EDC) System, and it will include rationale for changes. The EDC system has an audit trail, which will provide a complete record of the changes and corrections endorsed by the Investigator.

8.3.1. Data Queries

Programmed edit checks will be generated automatically, as the data is being entered into the system. Data Management will also run reports and listings on the CRF data, in addition to the queries already programmed and generated by the system, to raise manual queries as needed for site clarification or correction. The Clinical Dictionary Development and Management Group will raise queries as needed on safety data to code the terms (Adverse Events and Drugs) are reported appropriately.

The study monitor at the study site will review the CRFs in accordance with the monitoring plan, and any queries will be generated in the EDC System to the Investigator or designee, enabling the errors to be addressed in parallel with Data Management review. Monitor can also run reports and listings on the CRFs, to raise manual queries as needed for site clarification or correction

8.4. External Data

External Data are subject data obtained externally to the CRF. These data are generated from laboratory instruments, computers or other sources and then transcribed into a file and format agreed upon by GSKCH to identify the subject and time point referenced in the CRF and/or protocol.

Document Name	Clinical Protocol 207468.doc		
Type	Version	Document Identifier	Effective Date
eldo_controlled	3.0; Most-Recent; Effective; CURRENT	090032d580d15804	24-Mar-2017 07:31:33
Reason For Issue			Auto Issue

An agreed upon quality control process is performed against the transcribed data to the source to ensure the accuracy of the transcription. The transcribed data is transmitted in an agreed upon format to GSKCH via secured web portal or CD/DVD via mail carrier with tracking capabilities.

Proper reconciliation will be performed between the transcribed data and the clinical database to ensure subject and time point referenced in the Clinical Database match before Clinical Database Freeze (locking of the database) can occur.

9. STATISTICAL CONSIDERATIONS AND DATA ANALYSES

9.1 Sample Size Determination

Approximately 90 healthy subjects will be screened to randomise at least 72 subjects to ensure 66 subjects complete the entire study. This will ensure approximately 44 subjects per treatment arm (test product, positive control, no treatment) or 22 per treatment group (test product/no treatment, test product/positive control, positive control/no treatment). The sample size is based on clinical considerations. With 40 subjects, a difference between test product and untreated in the change from baseline in R_a of at least 46% of the magnitude of the within-subject standard deviation of the difference would be detectable at two-sided alpha=0.05 with approximately 80% power.

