The sample size is based on clinical considerations. With 40 subjects, a difference between test product and no treatment in the change from baseline in R_a of at least 46% of the magnitude of the within-subject standard deviation of the difference would be detectable at two-sided alpha=0.05 with approximately 80% power.

Diagnosis and Main Criteria for Inclusion

Healthy female volunteers, aged 30 to 65 (inclusive) with a Fitzpatrick phototype score of I-IV, presenting visible signs of ageing with a visual Clinical Fitzpatrick Wrinkle Score of Score 3-6 in the Periocular / Crow's Feet Area ~~with an equal rating~~ on both sides of the face (Appendix 3), with self-reported sensitive skin will be considered eligible to continue in the study.

Product Information

	Test Product	Reference Product
Product Name	Developmental Cosmetic Moisturising Cream	Olay ProX Wrinkle Smoothing Cream
Product Formulation Code (MFC)	CCI [REDACTED]	Commercially Available (UK)
Application Quantity	approx. 2 mg /cm ²	approx. 2 mg /cm ²
Route of Application	Dermal Topical	Dermal Topical
Application Instructions	Dispense two pumps of product (equating to approximately 0.6 mL) onto your fingertips and apply evenly to the randomly assigned side of the face, to include, the crow's feet area, cheek,	Subjects will be instructed to apply a pea-sized amount of the positive control product (equating to approximately 0.5g) onto your fingertips and apply evenly to the randomly assigned side of the face, to

Document Name	Clinical Protocol 207468.doc		
Type	Version	Document Identifier	Effective Date
eldo_controlled	3.0; Most-Recent; Effective; CURRENT	090032d580d15804	24-Mar-2017 07:31:33
Reason For Issue	Auto Issue		

	
forehead and chin twice daily, (morning and evening), after cleansing.
 
Daily applications should be approximately 8-12 hours apart.
 
Subjects will be reminded that as with all facial skin care products, care should be taken to avoid getting into the eyes. If contact does occur, then rinse thoroughly with water.
	
include the crow's feet area, cheek, forehead and chin, twice daily (in the morning and evening), after cleansing.
 
Daily applications should be approximately 8-12 hours apart.
 
Subjects will be reminded that as with all facial skin care products, care should be taken to avoid getting into the eyes. If contact does occur, then rinse thoroughly with water.

--	--	--

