9.2.3. Criteria for Evaluation

The primary objective will be to evaluate the change from baseline in wrinkle dimensions in the crow's feet area for the test product compared to no treatment after 4 weeks of twice daily product application. Given that this is a POC study, the study will be considered a success if at least a trend in favour of the test product is observed. There will be no adjustment to the critical alpha level of 0.05 to account for inflation due to multiplicity. P-values resulting from inferential testing will be considered primarily as summary statistics.

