9.3.2. Primary Analysis(es)

All efficacy analyses will be performed on the intent to treat (ITT) population.

Baseline and change from baseline in DermaTOP parameters R_a , R_z , S_a and S_{tm} will be summarised (N, mean, standard deviation, median, minimum and maximum) by treatment arm (test product, Olay ProX Wrinkle Smoothing Cream, no treatment) for each study visit (weeks 2 and 4). For each parameter, test product versus no treatment and positive control versus no treatment will be compared for the change from baseline at 2 weeks, and 4 weeks (primary endpoint), using analysis of covariance (ANCOVA) with subject (random effect), treatment, and side of face as main effects and baseline value as covariate. This approach allows for the inclusion of data from all subjects treated with a given treatment arm (test product, positive control or no treatment) regardless of the treatment group (test product/no treatment, test product/positive control, positive control/no treatment) to which they were randomised to derive estimates of treatment effect.

If the assumption of normality is rejected, an appropriate transformation to the data will be performed to facilitate the above method of analysis. Least square means from the ANCOVA model for the change from baseline will be presented for each treatment arm and pairwise treatment comparison, together with the 95% confidence intervals. In the absence of an appropriate data transformation, non-parametric analysis will be performed.

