### 4 Sample Size Determination

Approximately 90 healthy subjects will be screened to randomise at least 72 subjects to ensure 66 subjects complete the entire study. This will ensure approximately 44 subjects per treatment arm (test product, positive control, no treatment) or 22 per treatment group (test product/no treatment, test product/positive control, positive control/no treatment).

Document Name	Statistical Analysis CCI	207468.docx	
Type	Version	Document Identifier	Effective Date
eldo_clinical_doc	1.0; CURRENT; Most-Recent; Effective	090032d580d23463	10-Apr-2017 13:34:23
Reason For Issue	Auto Issue		

The sample size is based on clinical considerations. With 40 subjects, a difference between test product and untreated in the change from baseline in  $R_a$  of at least 46% of the magnitude of the within-subject standard deviation of the difference would be detectable at two-sided alpha=0.05 with approximately 80% power.

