### 8.1 Primary Analysis

The primary endpoint of the study will be change from baseline in Derma TOP parameter  $R_a$  at 4 weeks.

Baseline and change from baseline in DermaTOP parameters  $R_a$ ,  $R_z$ ,  $S_a$  and  $S_{tm}$  will be summarised (N, mean, standard deviation, median, minimum and maximum) by treatment arm (test product, Olay ProX Wrinkle Smoothing Cream, no treatment) for each study visit (weeks 2 and 4). For each parameter, test product versus no treatment and positive control versus no treatment will be compared for the change from baseline at 2 weeks, and 4 weeks, using analysis of covariance (ANCOVA) with subject (random effect), treatment, and side of face as main effects and baseline value as covariate. This approach allows for the inclusion of data from all subjects treated with a given treatment arm (test product, positive control or no treatment) regardless of the treatment group (test product/no treatment, test product/positive control, positive control/no treatment) to which they were randomised to derive estimates of treatment effect.

If the assumption of normality is rejected, an appropriate transformation to the data

Document Name	Statistical Analysis CCI	207468.docx	
Type	Version	Document Identifier	Effective Date
eldo_clinical_doc	1.0; CURRENT; Most-Recent; Effective	090032d580d23463	10-Apr-2017 13:34:23
Reason For Issue	Auto Issue		

may be performed to facilitate the above method of analysis. Least square means from the ANCOVA model for the change from baseline will be presented for each treatment arm and pairwise treatment comparisons, together with the 95% confidence intervals. In the absence of an appropriate data transformation, non-parametric analyses may be performed. In the event of the use of non-parametric analysis, median differences will be presented, together with 95% confidence intervals based on the Hodges-Lehmann method.

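### Does the 40-subject power sentence, in a design with 22 subjects per treatment pair, call for a change to the sample size section?

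*Protocol*

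**What the plan says.** Protocol 9.1 aims for 72 randomised subjects and 66 completers, counted as "44 subjects per treatment arm (test product, positive control, no treatment) or 22 per treatment group". It gives the basis in one line: "The sample size is based on clinical considerations". The power statement comes next and is worded for 40 subjects: taking test product against untreated skin on the change in R_a, a gap as large as "46% of the magnitude of the within-subject standard deviation of the difference would be detectable at two-sided alpha=0.05 with approximately 80% power". The synopsis and Protocol 3.3 carry the same statement ("With 40 subjects, a difference between test product and no treatment in the change from baseline in"), and SAP 4 repeats it ("With 40 subjects, a difference between test product and untreated in the change from baseline in").

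The primary comparison is made "using analysis of covariance (ANCOVA) with subject (random effect), treatment, and side of face as main effects and baseline value as covariate" (Protocol 9.3.2). SAP 8.1 describes the purpose of that model: "This approach allows for the inclusion of data from all subjects treated with a given treatment arm", whichever pair of treatments the subject received. Protocol 9.2.3 sets the bar: "the study will be considered a success if at least a trend in favour of the test product is observed". The same section gives p-values a mainly descriptive role.

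**The concern.** Forty is none of the planned counts (22, 44, 66 or 72), and neither document says whether it means within-subject pairs, subjects per arm or subjects in total. The reference to the SD of a within-subject difference is the language of a paired analysis, and a paired t-test on 40 differences returns the stated power. Only the test product/no treatment group yields that difference directly, and it has 22 completers. On its face, the trial seems to have little more than half the pairs behind its power claim.

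This is the only numerical statement of what the trial can detect on its primary contrast. If true power were near 54%, a null or marginal result would need to be read quite differently.

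**Working it through.** **Inputs.** From Protocol 9.1: 40 subjects, difference d = 0.46 of the SD of the within-subject difference, two-sided alpha 0.05, power about 80%, 66 completers, 22 per pair. From Protocol 9.3.2 and SAP 8.1: random subject effect, with treatment, side of face and baseline as further terms. Not given in either document: the between-side correlation of change from baseline (rho) and the correlation between baseline and change (r). Both are assumptions below.

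**1. The stated figure.** For a paired t-test the noncentrality is d × √n on n − 1 df.
- n = 40: 0.46 × √40 = 2.909 on 39 df, power 81.0%. The difference detectable with 80% power is 0.454 SD.
- n = 39: power 79.9%.

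So 40 is the smallest number of pairs that reaches 80%, and the stated figure is correct on that reading.

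**2. The direct pairs alone.** n = 22: 0.46 × √22 = 2.158 on 21 df, power 53.9%. This is the figure behind the concern, but it is not the planned analysis.

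**3. The planned model, leaving out the covariate.** Take six equal sequences and set the SD of the within-subject difference to 1. The information on test product minus no treatment, expressed as an equivalent number of direct pairs, has three parts:
- direct, from the test product/no treatment group: 22;
- indirect, through the positive control: the variance is 1/22 + 1/22, worth 11 pairs;
- between-subject: the sum of a subject's two sides has variance (1 + rho)/(1 − rho), and the test product/positive control group minus the positive control/no treatment group contributes 11 × (1 − rho)/(1 + rho).

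The total is 33 + 11 × (1 − rho)/(1 + rho). With noncentrality 0.46 × √(total) on 66 − 4 = 62 df:

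| Assumed rho | Equivalent pairs | Power at 0.46 SD | Detectable at 80% power (SD) |
|---|---|---|---|
| 0 | 44.0 | 85.2% | 0.43 |
| 0.35 | 38.3 | 80.0% | 0.46 |
| 0.5 | 36.7 | 78.3% | 0.47 |
| 0.7 | 34.9 | 76.3% | 0.48 |
| 0.9 | 33.6 | 74.7% | 0.49 |
| limit 1 | 33.0 | 73.9% | 0.495 at rho 0.99 |

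The model is worth exactly 40 pairs when 11 × (1 − rho)/(1 + rho) = 7, that is rho = 4/18 = 0.22.

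**4. The baseline covariate.** If adjustment multiplies the residual variance by 1 − r², 80% power with 66 completers is restored at r of about 0.21, 0.30 and 0.35 for rho 0.5, 0.7 and 0.9 (61 df). In simulations that fitted the full model by REML (10,000 trials per setting, with baseline given the same rho as change), r = 0.4 gave 90.9%, 85.9%, 85.4% and 81.5% at rho 0, 0.35, 0.5 and 0.9. With r = 0.2 the results were 87.2%, 81.6%, 79.6% and 76.1%.

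**5. Other readings of 40.** Forty per arm (60 subjects) under the step 3 model gives 81.6% at rho 0, stays at 80% or more up to rho of about 0.09, and falls to about 70% in the limit. Treating 40 sides per arm as independent, with the SD of the difference equal to √2 times the SD of one side, gives 81.9%. Forty subjects in total would give 52% to 64%, but the same paragraph plans 66 completers.

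**The case for a change.** The strongest case for a change is that the sentence cannot be traced to the trial. It stands in four places, none of them says what 40 counts, and no power is given for the model that will be fitted. Without a covariate gain, that model reaches 80% only if rho is at most about 0.35. The two sides of one face may well correlate more strongly, which would leave power near 75%. The sponsor cannot rely on an unstated covariate gain to fill the gap, and a replacement sentence would cost little.

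The first part stands: the 40 is undefined and the planned model's power is not shown. The rest carries less weight. The worst shortfall before adjustment is about 6 points (80 − 74). Whether any shortfall exists depends on two correlations that the documents do not give. A replacement sentence would have to rest on the same unknown correlations, so it would exchange one undocumented figure for a range on assumed values. Nor is it true that no literal reading reaches 80%: forty per arm does so when rho is close to 0.

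**Conclusion.** The concern does not call for a change. The arithmetic is sound on its natural reading (81.0% with 40 pairs), and the contrast with 22 pairs overlooks that the planned model also uses the other two groups. With 66 completers the model is worth 33 to 44 direct pairs, and power at 0.46 SD is about 74% to 85% before any benefit from the covariate, so the claimed power is roughly met. What remains is a missing explanation of one number.

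Nothing in the trial depends on that explanation. The size is attributed to clinical considerations rather than to this calculation, the analysis is fully specified without it, and success requires only a trend. A statistician interpreting the result will use the confidence interval from the fitted model, which carries the actual precision.

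The conclusion assumes 66 completers spread evenly over the six sequences, a common variance on both sides of the face, and rho anywhere between 0 and 1.

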9.2. General Considerations

9.2.1. Definition of Analysis Populations

The ‘Intent to treat’ (ITT) population includes all subjects who are randomised into the study and have at least one post-baseline clinical assessment available. All efficacy analyses will be based on the ITT population.

The Per Protocol (PP) population will consist of the subset of ITT subjects which excludes those subjects with significant protocol deviations. Protocol deviations will be identified prior to database unblinding and will include, but not be limited to, non-compliance with the protocol or product application and use of prohibited

Document Name	Clinical Protocol 207468.doc		
Type	Version	Document Identifier	Effective Date
eldo_controlled	3.0; Most-Recent; Effective; CURRENT	090032d580d15804	24-Mar-2017 07:31:33
Reason For Issue	Auto Issue		

concomitant medications. Confirmatory analyses of at least the primary efficacy endpoint of DermaTOP R_a will be performed on the PP population.

The Safety population will include all subjects with at least one product application to either side of the face. All safety analyses will be performed using the Safety population.

9.2.2. Exclusion of Data from Analysis

No data will be excluded from any analysis.

